#### Column 4 - Activity with Leakage & Was Urge Present:

Describe the activity associated with the leakage i.e. coughing, sneezing, bending, lifting, running, jumping, hearing running water, going outside, having a strong urge.

Describe the urge sensation you had to go as:

MILD= first sensation or desire to go.

MODERATE = stronger sensation or desire to go.

STRONG = a very strong sensation or desire to go or get to toilet, move aside!

Inflammation in Women with Urgency Urinary Incontinence Treated with Anticholinergics

Version Date: 7/28/2022

ID: 2018P000980

Study Name: Inflammation in Women with Urgency Urinary Incontinence Treated with Anticholinergics

PI Name: [name]

Prepared by: [name], B.S., Research Assistant

Specific Aim 1: To assess inflammatory markers in urine and serum before and after a 6-week treatment course with anticholinergics.

Specific Aim 2: To determine the role of the urinary microbiome in relation to inflammation before and after a 6-week treatment course with anticholinergics.

Study Population: This study is a prospective pilot of women who have a diagnosis of urge urinary incontinence (UUI) and present to the BWH Urogynecology Clinics in Boston or Foxborough. This study enrolled 20 women offered standard of care anticholinergic treatment for 6 weeks.

Statistical Methods: Demographic and clinical characteristics were summarized with the absolute count and percent of categorical variables and median and interquartile range of continuous variables. No comparison was made as demographic and clinical characteristics did not change in follow-up period.

Plasma and combined (baseline and follow-up) urine cytokines were summarized using median and interquartile range.

Urine cytokines at baseline and follow-up were tested for normality using Shapiro-Wilks test for normality. The data were found to be non-normal and thus were summarized using median and interquartile range. Urine cytokines were compared from baseline to follow-up for most patients (only 13 of the 20 patients returned for follow-up) using t-test of Wilcoxon rank sum. P value of <0.05 was considered significant.

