## VI: Statistical Considerations

Descriptive statistics will be employed to describe and compare data using parametric statistical tests for normally distributed data and non-parametric tests for non-normally distributed data. We will then specifically evaluate the role of microbiome on UUI in our subgroups. Wilcoxon test and Mann Whitney test will be applied to estimate the possible differences. The correlation between microbiome and inflammatory markers before and after treatment will be assessed by the Spearman's rank correlation. Harvard Catalyst Statisticians will be consulted for statistical analysis.

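### The SAP checks normality of urine cytokines visit by visit and describes no analysis of within-woman change, although the comparison rests on 13 women measured twice; one paired analysis of log ratios would fit the question better

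*SAP*

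**What the plan says.** The SAP's Statistical Methods describe four steps for urine cytokines.

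- **Normality check:** "Urine cytokines at baseline and follow-up were tested for normality using Shapiro-Wilks test for normality".
- **Consequence:** "The data were found to be non-normal and thus were summarized using median and interquartile range".
- **Comparison of baseline with follow-up:** "using t-test of Wilcoxon rank sum", in a study where "only 13 of the 20 patients returned for follow-up".
- **Threshold:** "P value of <0.05 was considered significant".

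Protocol section VI gives the general rule: "parametric statistical tests for normally distributed data and non-parametric tests for non-normally distributed data". It adds that "Wilcoxon test and Mann Whitney test will be applied to estimate the possible differences", without saying which kind of Wilcoxon test is meant or which comparison each test serves.

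Neither document mentions a within-woman change, a transformation, a ratio or difference with a confidence interval, or a rule for values below detection. That the analysis was on the raw concentration scale is inferred from this silence; it is not stated.

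**The concern.** Specific Aim 1 asks how markers move over six weeks of treatment in the same women. A paired t-test assumes roughly normal within-woman differences, and a signed-rank test assumes that they are roughly symmetric. Neither assumption concerns the distribution at a single visit, so a visit-level Shapiro-Wilk test checks the wrong quantity.

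The scale matters too. If cytokines change proportionally, the women with the highest concentrations have the largest raw differences and dominate a t-test, and they take the top ranks in a signed-rank test. Log ratios put the women on a common footing.

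At stake are some power in a sample already down to 13 pairs, and the lack of any estimate of effect. Two medians with interquartile ranges do not tell a reader by what factor a cytokine changed, or how precisely that is known.

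**Working it through.** **Inputs from the documents.** 20 women enrolled and 13 returned, so 13/20 = 65% can contribute a pair (assuming that all 13 have a usable baseline sample). The threshold is 0.05, taken as two-sided. The documents contain no power figure to reproduce.

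**Assumed inputs (not in the documents).** Log-normal concentrations with proportional change; log SD 0.5 to 1.5; baseline to week 6 correlation of the logs 0 to 0.7; standardised log change dz = mean log change / SD of log change = 0.6 or 0.85, which gives about 50% or 80% power for a paired t-test with 13 pairs. The counter-case is a log-normal baseline with additive change and normal within-woman error.

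**Method.** Simulation of 13 pairs, 10,000 replicates per setting (standard error at most √(0.25/10,000) = 0.5 points). The signed-rank test is exact, with critical value 17 and true two-sided level 0.0479.

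**Selected settings, power in %:**

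| Change | Log SD | Corr. | dz | Rank-sum | Signed-rank, raw | Signed-rank, log ratio | Paired t, raw | Paired t, log ratio |
|---|---|---|---|---|---|---|---|---|
| Proportional | 1.5 | 0 | 0.6 | 50.4 | 42.8 | 48.3 | 21.4 | 50.9 |
| Proportional | 1.2 | 0.7 | 0.85 | 26.2 | 69.5 | 78.9 | 41.6 | 81.1 |
| Proportional | 1.5 | 0.7 | 0.85 | 26.1 | 66.4 | 77.8 | 29.0 | 79.9 |
| Additive | 0.8 | – | 0.85 | 0.1 | 78.5 | 70.7 | 80.4 | 42.6 |
| Additive | 1.2 | – | 0.85 | 0.0 | 76.4 | 66.1 | 78.5 | 29.2 |

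**Over the whole proportional grid:**

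- Signed-rank, log ratio minus raw: +1.6 to +11.4 points. It reaches 10 only at log SD 1.5, correlation 0.5 or more and dz 0.85.
- Paired t on log ratios minus signed-rank on raw differences: +3.7 to +13.5 points.
- Paired t, log ratio minus raw: +5 to +51 points.
- Rank-sum, log minus raw: exactly 0, because logging does not alter ranks.
- Paired t on log ratios minus rank-sum: about 0 at correlation 0, +13 to +16 at 0.3, +28 to +30 at 0.5, +42 to +55 at 0.7.
- Type I error of the log-ratio tests: 4.5% to 5.4%.

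**A second parameterisation.** Fix the SD of the log change at 0.7 and vary the between-woman log SD b from 0.3 to 1.6. With equal independent error at each visit, the error variance per visit is 0.7²/2 = 0.245 and the correlation is b²/(b² + 0.245), which runs from 0.09/0.335 = 0.27 to 2.56/2.805 = 0.91. A log change of −0.5 is a fall of 1 − exp(−0.5) = 39%. The signed-rank gain from log ratios is about 3 to 13 points. For a 39% fall, rank-sum has 0.5% to 54% power and paired t on log ratios 65% to 66%. For b from 0.8 to 1.6, raw visit values fail Shapiro-Wilk in 72% to 95% of samples, while log ratios fail in about 5%.

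**What the log-ratio analysis would report.** With log ratios d, the estimate is exp(mean d) and the 95% CI is exp(mean d ± 2.179 × s/√13). At an observed mean of −0.5 and s = 0.7, the half-width is 2.179 × 0.7/3.606 = 0.423, so the ratio is 0.61 (0.40 to 0.93).

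**Non-detects.** A floor weakens the log t-test. In one setting (between-woman log SD 0.8, error SD 0.5 per visit, dz 0.6) its power falls from 51.9% with none to 44.2% and 34.7% at assumed non-detect fractions of 0.2 and 0.4.

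**The case against.** The strongest objection is that the only rank test the SAP names is rank-sum, which a log transform cannot change. On that reading the main defect is the unpaired or unclear test, and scale matters only once pairing is settled. This stands. The SAP's wording also admits a t-test, which does depend on scale, but the gain over rank-sum comes from pairing.

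Four stronger readings are tempting, and the documents do not support them.

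- *A fixed gain of 10 points or more.* No SD, correlation or effect size is given, and gains of that size need strongly skewed data, in most settings with a high correlation between visits.
- *A free gain.* With additive change, log ratios lose 6 to 10 points (signed-rank) or 25 to 49 points (paired t). Results also depend on the non-detect floor, and the target becomes a ratio.
- *That Shapiro-Wilk chose the test.* The SAP ties non-normality only to the summary statistics. The protocol's general rule makes the link plausible, but it is not stated.
- *That the reported comparison is wrong.* The documents give no results to judge. Under positive correlation rank-sum errs towards missing changes: its type I error was about 0.9% at correlation 0.5 (log SD 1.0).

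It can also be said that choosing a scale after seeing the data is post hoc. This stands too, since the SAP is written in the past tense and already reports the normality result. It is a reason to label the re-analysis, not to leave change unanalysed.

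**Conclusion.** The point holds in a limited form. Normality was assessed on visit values when the question concerns 13 within-woman changes, and the SAP describes no analysis or estimate of those changes. This follows from the text and needs no simulation.

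The size of the benefit is an assumption. If changes are proportional and roughly log-normal, log ratios add about 2 to 13 points of power over a signed-rank test on raw differences, and 5 to 51 points over a raw paired t-test. Against rank-sum, logging adds nothing; pairing adds from about zero with uncorrelated visits to 55 points at correlation 0.7. If changes are additive, the log scale is the worse choice, and the documents do not say which form applies. The more secure benefit is a fold change with a confidence interval. The change is worth making, but it comes second to stating that the test is paired.

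**What to change.** Replace the visit-level Shapiro-Wilk step and the comparison sentence in the SAP with text such as:

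> For each urine cytokine, log(week 6/baseline) will be computed in each of the 13 women with both samples. One paired method is used for all cytokines: a paired t-test on the log ratios, with the exact signed-rank test on the log ratios as a sensitivity analysis. The geometric mean ratio is reported with its 95% CI. Values below detection are set to one common floor per cytokine at both visits. For cytokines mostly below detection, detection rates at each visit are reported instead. This analysis was specified after the data had been examined and is post hoc.

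Any check of distribution should look at the 13 log ratios and should not switch the method. A signed-rank result on raw differences, shown alongside, guards against additive change. Pairs at the floor at both visits give zero log ratios, so the signed-rank test must use the exact distribution for the pairs that remain.

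The cost is SAP wording and a re-run on existing data, with no new samples or visits. The downsides are dependence on the floor and lower power if changes are additive.

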## V. Outcome measures

- a. **Primary outcome:** To assess if the urinary microbiome is associated with inflammatory and immune changes in women with UUI.
- b. **Secondary outcomes:** To assess the effectiveness of anticholinergic treatment in relation to the urinary microbiome and immune status over a 6-week course, and to investigate if the interaction of urinary microbiome with host through immunologic markers may alter responsiveness to standard of care treatment with anticholinergics.

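### The SAP was finalised after the data were examined; it tests only a Specific Aim 1 comparison at P<0.05 and gives no method for the protocol's primary outcome

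*SAP*

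**What the plan says.** The SAP header carries "Version Date: 7/28/2022". Its Statistical Methods paragraph is written in the past tense and includes findings. On the urine cytokines it says "The data were found to be non-normal and thus were summarized using median and interquartile range", and on follow-up it says "only 13 of the 20 patients returned for follow-up".

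It describes one inferential comparison: "Urine cytokines were compared from baseline to follow-up for most patients", carried out "using t-test of Wilcoxon rank sum". The criterion is "P value of <0.05 was considered significant". Everything else in that paragraph is descriptive, apart from the Shapiro-Wilk check of distribution.

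Protocol Section V gives the primary outcome as "To assess if the urinary microbiome is associated with inflammatory and immune changes in women with UUI". The secondary outcomes have two parts. One is "To assess the effectiveness of anticholinergic treatment in relation to the urinary microbiome and immune status over a 6-week course". The other is whether interplay between the microbiome and the host's immune markers changes response to treatment.

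Protocol Section VI plans to choose parametric or non-parametric tests by normality. It names Wilcoxon and Mann-Whitney tests, and plans a Spearman correlation of microbiome with inflammatory markers before and after treatment. It states no significance level.

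**The concern.** A stated threshold with the word *significant* normally signals an error rate fixed before the data were seen. Here the threshold and the named test enter the record in a document that already reports the distribution of the variable being tested. The one comparison that receives a P value is also not the outcome the protocol calls primary.

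Two things are at stake. The first is how much weight a cytokine P value below 0.05 can bear. The second is that someone reading only the SAP would not learn that the analysis matching the primary outcome is missing. The SAP restates Specific Aim 2, on the microbiome, and then gives no method for it.

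**Working it through.** The documents give no power, effect size or standard deviation, so there is no design figure to reproduce. The check is mainly a comparison of texts.

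**1. Timing.** Two statements in the SAP could not be known before follow-up ended and the cytokines were examined: the non-normality finding and the count of returning women. Follow-up was 13/20 = 65%, with 7/20 = 35% missing. The remark that demographic and clinical characteristics did not change is not relied on here. Many of those variables (race, parity, past surgery) would not be expected to change in six weeks, so it need not reflect inspection of data.

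**2. What was planned and what the SAP covers.**

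| Protocol item | In the SAP |
|---|---|
| Specific Aim 1: markers before and after treatment | Urine comparison tested |
| Section V primary: microbiome and inflammation | No method |
| Section V secondary, part 1: effectiveness in relation to microbiome and immune status | No method; no UDI-6 or diary measure |
| Section V secondary, part 2: microbiome-host interaction and response | No method |
| Section VI: choice of test by normality | Shapiro-Wilk applied; resulting test unclear |
| Section VI: role of microbiome in subgroups | Absent |
| Section VI: Spearman correlation | Absent |

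So 0 of 3 Section V outcomes have a method in the SAP, and the single tested comparison comes from Aim 1.

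**3. What is new in the SAP.** The 0.05 level has no earlier source. Section VI does not tie its Wilcoxon test to before/after marker levels. The SAP's wording leaves open whether a t-test, a rank sum test or a mixture was used. Rank sum is a test for independent groups, whereas this comparison is within women. Because Section VI lists Wilcoxon separately from Mann-Whitney (the rank sum test under another name), it probably meant the paired signed-rank test; that is an inference.

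**4. Illustration of the error rate.** The documents do not say how many cytokines were tested, and they mention no multiplicity adjustment. For k independent tests, each at 0.05, the chance of at least one false positive is 1 − 0.95^k:

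- k = 1: 5.0%
- k = 5: 1 − 0.95^5 = 22.6%
- k = 10: 1 − 0.95^10 = 40.1%
- k = 20: 1 − 0.95^20 = 64.2%

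Both k and independence are assumptions. Positively correlated cytokines would usually give lower figures.

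**The case against.** A reader might infer that the cytokine comparison was post hoc, with endpoint, test and threshold all first set down once the data were visible. The documents do not support that. Before/after assessment of inflammatory markers is Specific Aim 1 of the protocol. Sections III and IV plan catheterised urine for these markers at both visits. Section VI had already set the normality rule and named the Wilcoxon and Mann-Whitney tests, and a normality check followed by a rank test broadly follows that rule. The 0.05 level is conventional, and nothing suggests that it was chosen in response to the data.

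A reader might also infer that the SAP presents the cytokine change as the primary result, or that the Spearman analysis was dropped because of what it showed. Neither is in the text. The SAP never calls the comparison primary or confirmatory, its past tense is open about timing, and the study is described throughout as a pilot. Whether the correlation was ever run is not stated.

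Finally, leaving the Section V outcomes untested does not by itself alter the error rate of an Aim 1 test.

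All of this stands, and it limits the point. It does not explain why the primary outcome has no method, and it does not supply an earlier source for the threshold or the exact test.

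**Conclusion.** The point holds in limited form. This SAP version was finalised after data review. Its one inferential comparison is a planned Aim 1 analysis that Section V does not list as an outcome. Only three things are new in it: the 0.05 threshold, the exact test, and the position of this comparison as the sole one tested. The weightier gap is that the primary outcome has no method, although a matching analysis was planned.

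The size in terms of coverage is 0 of 3 Section V outcomes. The inflation of the error rate cannot be determined; the 22.6% to 40.1% range for 5 to 10 cytokines is illustrative only.

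The conclusion rests on two assumptions. The first is that the protocol preceded enrolment: no date is visible in the text, but it is written in the future tense. The second is that no earlier SAP exists with the missing methods; none is among the documents. The matter should be corrected before any cytokine P value is described as significant.

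**What to change.** In the SAP's Statistical Methods:

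- Replace the significance sentence with, for example: *P values are exploratory. The before/after urine cytokine comparison is a Specific Aim 1 analysis and is not the primary outcome.*
- State that the document was written after the data had been reviewed. A change of title alone would achieve nothing.
- Name the test actually used for the before/after comparison.
- Report the Spearman correlation of microbiome with inflammatory markers as the primary-outcome analysis, using up to 20 women at baseline and up to 13 at follow-up, or state that it was not done and why. If the microbiome summary measure is chosen now, say so and treat that result as exploratory too.
- Add a table listing each Section V outcome and each Section VI analysis as done, changed or not done, with a reason for each change or omission.

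The cost is a weaker headline claim and a little more analysis work. No new patients or samples are needed if the planned microbiome assays were completed, which the SAP does not say.

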### **III. Research Design and Methods**

#### ***Study design, population, and inclusion/exclusion criteria***

This study is designed as a prospective pilot research of women presenting to our Urogynecology Clinic in our Boston or Foxborough locations with UUI symptoms. The inclusion criteria are women who have a diagnosis of UUI and are willing to participate in the study and provide their blood and urine for research purposes. The exclusion criteria are: lack of consent, neurological disease such as Parkinson's or Multiple Sclerosis, known immunological deficiencies, history of UTI in the last 3 months, history of taking anticholinergics within the last month, history of antibiotics use in the last month, history of sexually transmitted diseases.

We plan to enroll 20 women who are offered treatment with a standard of care anticholinergic medication for 6 weeks. The patient's provider will explain the study to eligible patients and consent will be obtained by the research assistant. Once consent is obtained, a catheterized urine sample will be collected from the patient as well as a blood draw by the phlebotomist at the Center of Clinical Investigation at Brigham and Women's Hospital or at the phlebotomy lab at The Brigham Health and Brigham and Women's/Mass General Health Care Centers in Foxborough. Participants will be asked to fill the UDI-6 questionnaire and they will be given a two-day diary to complete at home before they start the anticholinergic medication. They will be then asked to follow up 6 weeks later. Prior to the 6-week follow-up visit, participants will fill another 2-day voiding diary and complete the UDI-6 questionnaire. At the 6-week visit, a repeat catheterized urine sample will be taken for microbiome and inflammatory markers analysis but no blood draw. The urine will be assessed by enhanced urine cultures and DNA sequencing for urinary microbiome at baseline and again at 6 weeks. Inflammatory mediators will also be tested in urine and blood. The microbiome analysis and bioinformatic analysis will be performed by two experienced Harvard Research Core Labs. Inflammatory mediators will be tested by a third Research Core Lab at Boston University. Baseline urinary symptoms at enrollment and variation of symptoms after 6 weeks of anticholinergic treatment will be assessed using a two-day bladder diary and a validated UI questionnaire (UDI-6).

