### **IV. Study procedures**

- a. **Visit of enrollment:** Participants presenting with UUI diagnosis will complete the informed consent document and a baseline UDI-6 questionnaire. (Appendix A). This survey consists of 6 questions to assess the nature and severity of urinary incontinence symptoms at baseline. In addition, participants will be asked to provide urine sample for microbiome and immune markers and blood samples solely for immune markers. Participants will be given 2-day bladder diaries to fill out at home and before starting anticholinergic treatment.
- b. **Randomization/treatment allocation:** Randomization will not be performed. All patients will receive treatment with anticholinergics for a duration of 6 weeks.
- c. **Follow up visit after 6 weeks:** Participants will complete another 2-day voiding diary prior to their visit and they will be asked to bring the diaries to their visit. They will also complete the UDI-6 questionnaire to assess changes in urinary symptoms after 6-weeks of anticholinergic treatment. Patients will be evaluated for drug effectiveness by the treating urogynecologist. Urine will be taken for repeated analysis of microbiome and immune markers.

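### The SAP names an unpaired rank-sum test, alongside an undefined t-test, for cytokines measured twice in the same women; it should say which test was run and on whom, and name a paired test.

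*SAP*

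**What the plan says.** The design has one group measured twice. Protocol section IV states "Randomization will not be performed. All patients will receive treatment with anticholinergics for a duration of 6 weeks". Under Study design in section III, at 6 weeks "a repeat catheterized urine sample will be taken for microbiome and inflammatory markers analysis but no blood draw", and the follow-up visit in section IV repeats this: "Urine will be taken for repeated analysis of microbiome and immune markers".

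On testing, Protocol section VI calls for "parametric statistical tests for normally distributed data and non-parametric tests for non-normally distributed data" and adds "Wilcoxon test and Mann Whitney test will be applied to estimate the possible differences". It ties neither of those two tests to a particular comparison.

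The SAP is written in the past tense. After Shapiro-Wilk testing at each visit it reports "The data were found to be non-normal and thus were summarized using median and interquartile range". It continues "Urine cytokines were compared from baseline to follow-up for most patients", and the parenthesis and test name follow: "only 13 of the 20 patients returned for follow-up) using t-test of Wilcoxon rank sum". Significance is set at P < 0.05. Neither document uses the word paired or the term signed-rank.

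**The concern.** Each returning woman supplies both a baseline and a follow-up value, and the question is whether her value changed. Rank-sum (Mann-Whitney) treats the two sets of values as coming from different people. Its P value is correctly calibrated on such data only if a woman's two values are uncorrelated. With positive correlation the test is conservative and a real change can be missed. With negative correlation it rejects too often.

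Two further points are open. The t-test has no stated form and no rule for when it applies, although the same paragraph reports non-normal data. The analysis set is also not fixed. The wording leans towards the 13 returners, but an unpaired test could equally take 20 baseline values against 13 follow-up values. In that case any baseline difference between the 7 non-returners and the 13 returners would be mixed with change over time. Nor does the SAP say how many of the 13 had usable urine at both visits.

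This is the only between-visit comparison the SAP describes, and it covers the urine part of Specific Aim 1. It is not the primary outcome in Protocol section V. A null finding is the result most exposed.

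**Working it through.** **Inputs from the documents.** 20 enrolled and 13 returned (13/20 = 65%), so 7 had baseline only (7/20 = 35%). The threshold is P < 0.05, taken here as two-sided. The documents give no power calculation, within-woman correlation r, SD or effect size, so there is no stated figure to reproduce. All values of r and shift below are assumptions.

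**Why calibration fails.** This is an approximation for a difference in means with equal SDs at both visits.

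- *13 v 13.* An unpaired test assumes variance 2σ²/13. The true variance is 2σ²(1 − r)/13. The ratio of true to assumed standard error is √(1 − r), so the effective critical value is 1.96/√(1 − r).
  - r = 0.5: 1.96/0.707 = 2.77, two-sided error 0.6%.
  - r = 0.3: 1.96/0.837 = 2.34, error 1.9%.
  - r = −0.3: 1.96/1.140 = 1.72, error 8.6%.
- *20 v 13.* Only 13 of the 20 baseline values are paired. The assumed variance is σ²(1/20 + 1/13) = 0.1269σ². The true variance is σ²(1/20 + 1/13 − 2r/20).
  - r = 0.5: √(0.0769/0.1269) = 0.778, critical value 2.52, error 1.2%.
  - r = 0.3: √(0.0969/0.1269) = 0.874, critical value 2.24, error 2.5%.

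**Simulation with the actual rank tests.** 20,000 trials per setting, bivariate normal values without ties, exact two-sided tests at 0.05. Each cell gives rank-sum 13 v 13 / rank-sum 20 v 13 / signed-rank on 13 pairs, in %.

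| r | Type I error | Power, 0.5 SD shift | Power, 0.8 SD shift |
|---|---|---|---|
| −0.3 | 7.2 / 7.1 / 4.8 | 23.4 / 27.5 / 16.7 | 46.0 / 55.0 / 35.8 |
| 0 | 4.2 / 4.6 / 4.5 | 20.5 / 25.4 / 20.6 | 46.1 / 55.7 / 45.0 |
| 0.3 | 1.9 / 2.5 / 4.9 | 17.1 / 23.6 / 27.4 | 44.7 / 56.0 / 58.5 |
| 0.5 | 0.8 / 1.2 / 4.7 | 14.3 / 21.3 / 36.5 | 45.4 / 57.3 / 73.0 |
| 0.7 | 0.2 / 0.5 / 4.7 | 10.7 / 18.8 / 54.6 | 46.2 / 59.1 / 91.2 |

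A separate run of the same settings agreed within simulation error.

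Power lost by rank-sum against signed-rank for a 0.8 SD shift:

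- r = 0.3: 58.5 − 44.7 = 13.8 points (13 v 13), or 58.5 − 56.0 = 2.5 points (20 v 13).
- r = 0.5: 73.0 − 45.4 = 27.6 points (13 v 13), or 73.0 − 57.3 = 15.7 points (20 v 13).

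**If the 7 baseline-only women differ.** Suppose no woman changes, but the 7 sit 1 SD away from the returners at baseline. Rank-sum 20 v 13 then rejects in 12.4%, 8.8% and 6.4% of trials at r = 0, 0.3 and 0.5. With a 0.5 SD difference the figures are 6.7%, 4.3% and 2.8%. Signed-rank on the 13 pairs does not use those 7 values and stays near 5%.

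**Limits.** Ties and values at a detection limit are not modelled. Signed-rank, unlike rank-sum, depends on the scale. With log-normal values and differences taken on the raw scale, its power for the 0.8 SD shift falls to about 53% at r = 0.3 and 66% at r = 0.5. At r = 0.3 that is slightly below rank-sum 20 v 13.

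**The case against.** The best counter-argument is that this is a slip of wording. The phrase is garbled, probably with *of* typed for *or*. Protocol section VI lists a Wilcoxon test separately from Mann-Whitney; since Mann-Whitney is the rank-sum test, the other is most naturally signed-rank. The parenthesis reads as an explanation of why only 13 women were compared, which makes 20 v 13 unlikely. Nothing in the documents suggests that the 7 differed or that any samples were unusable. The study is a 20-woman pilot with no power claim, and this is not its primary outcome. A paired t-test could also be sound, because Shapiro-Wilk was applied to the values at each visit, not to within-woman differences or logs.

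Much of this is fair. The slip is plausible, the 13 returners are the likelier set, and the size of any effect rests wholly on assumed r and shift. A paired t-test on log differences that look roughly normal could be defended.

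It does not cure the text. Section VI assigns neither test to this comparison, so it cannot show what was run. The SAP describes completed work, and taken at its word it reports an unpaired test on paired data. A defensible paired t-test does not rescue an unspecified one, and the protocol's own rule combined with the reported non-normality points to a non-parametric test.

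**Conclusion.** The concern holds. As written, the test does not match the design, and a reader cannot tell which test was run or on which women. The point needs correcting because of the wording of the comparison; no effect on results has been shown.

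If rank-sum was run on the 13 returners, the size depends on r. At r = 0 there is no loss. At r = 0.3 to 0.5 the true type I error is about 2% to 1%, and about 14 to 28 points of power are lost for a 0.8 SD shift. At r = −0.3 the type I error is about 7%. If it was run 20 v 13, the loss at r = 0.3 to 0.5 is about 2.5 to 16 points, and at r = 0 rank-sum has more power. Those 20 v 13 figures hold only if the 7 baseline-only women resemble the returners; otherwise drop-out is confounded with change. The power comparison also assumes that differences are taken on a scale where they are symmetric.

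A paired test makes the comparison valid for the women who returned. It does not remove possible bias from losing 7 of 20.

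**What to change.** 1. Check the analysis code or output. State in the SAP which test was run and whether the 7 baseline-only women entered it.
2. If signed-rank was run, replace the test name with: *Wilcoxon signed-rank test on within-woman differences, in women with usable urine at both visits (n = __, at most 13)*.
3. If rank-sum or a t-test was run, say so. Rerun signed-rank on the existing data, show both P values, and label the new one as a correction made after the data were seen.
4. Delete the t-test option, in line with section VI of the protocol and the reported non-normality.
5. Show the baseline median and IQR for the same women who contribute the follow-up median and IQR.
6. Report the measurement scale, the handling of ties and of values at the detection limit, and the effect estimate, as actually done. These choices remain the sponsor's.

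The cost is one check, one SAP phrase and, if an unpaired test or a t-test was used, a rerun on existing data.
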